### **7.1.2 Dosage and method of administration**

No drug trials were involved in this study.

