## 8. Discontinuation of the research intervention and discontinuation/withdrawal of research subjects

### 8.1 Discontinuation of the research intervention

The investigator should consider discontinuing the study intervention if the subject develops.

1) patients with serious unintended adverse reactions or complications that do not improve significantly after symptomatic treatment and cannot be continued. patients who are unable to continue the study intervention.

2) Patients who are unable to tolerate the study intervention for non-treatment related reasons.

3) Laboratory test values that, in the judgment of the investigator, are clinically significant. After discontinuation of the study intervention, patients may continue to complete other parts of the treatment regimen, including chemotherapy, radiotherapy, targeted therapy, immunotherapy, etc., and will be treated in accordance with the study protocol. therapy, targeted therapy, immunotherapy, etc., and will be scheduled for examination and follow-up according to the study protocol.

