### 8.2 Suspension/withdrawal of research subjects

The researcher may discontinue or withdraw a research subject if the subject is.

1) pregnancy

- 2) apparent noncompliance with the study intervention.
- 3) if clinical side effects, abnormal laboratory tests, or other clinical conditions occur that make continued participation in the study is no longer in the best interest of the subject.
- 4) Disease progression such that discontinuation of the study intervention is warranted.
- 5) The subject meets the exclusion criteria (emerging or confirmed).
- 6) the subject is unable to receive the study intervention for a certain period of time.

The reason for discontinuation/withdrawal of the subject from the study should be documented on the case report form, and subjects who signed the informed consent, were randomized, but did not receive the study intervention will be replaced. Subjects who signed informed consent, were randomized, received the study intervention and were subsequently withdrawn will or will not be replaced.

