## 9.3 Adverse Events and Serious Adverse Events

### 9.3.1 Definition of Adverse Events (AE)

This refers to all adverse medical events that occur after a subject has undergone radical lung cancer surgery, which may be manifested by signs, symptoms, disease, or abnormal laboratory tests, but are not necessarily causally related to the trial intervention.

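### The replacement rule in section 8.2 cannot be applied as written: it assumes randomization, leaves one case undecided, and rests on a study intervention that the protocol describes inconsistently

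*Protocol*

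**What the plan says.** Protocol section 8.2 has two replacement sentences. Consenting subjects who "were randomized, but did not receive the study intervention will be replaced". Those who "received the study intervention and were subsequently withdrawn will or will not be replaced". Both sentences are limited to randomized subjects, whereas sections 6.4 and 7.3 say that the study has one arm, no allocation and no randomization.

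Withdrawal is at the researcher's discretion: "The researcher may discontinue or withdraw a research subject if the subject is" in one of six situations. These include side effects, a newly met exclusion criterion, "Disease progression such that discontinuation of the study intervention is warranted", and the case where "the subject is unable to receive the study intervention for a certain period of time".

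On the intervention itself, section 7.1.1 carries the heading for its description. It runs from work-up through chemoimmunotherapy and reassessment to surgery, with pneumonectomy among the permitted operations. Other sections point to surgery alone:
- Section 7.1.2: "No drug trials were involved in this study".
- Section 8.1: "After discontinuation of the study intervention, patients may continue to complete other parts of the treatment regimen, including chemotherapy".
- Section 9.3.1 defines adverse events as "all adverse medical events that occur after a subject has undergone radical lung cancer surgery".

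Sections 1.1, 5.2 and 9.1 name the R0 resection rate by lobectomy as the primary endpoint, and section 9.1 evaluates it from postoperative specimens. Sections 5.1 and 5.3 give 50 patients, without a calculation.

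**The concern.** A replacement rule decides who fills the 50 places and when recruitment stops. Sites apply it while the trial runs, so a later analysis plan cannot supply it.

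The objective is feasibility: in how many patients who need pneumonectomy at diagnosis can a complete resection by lobectomy be achieved after chemoimmunotherapy? A patient who progresses or deteriorates on that therapy and is never operated on is a failure of the strategy. The grounds for withdrawal in section 8.2 cover such patients. One example is the newly met exclusion criterion, since the first exclusion in section 6.2 is organ dysfunction that makes surgery intolerable.

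With the rule unsettled, whether to replace such a patient can be decided after the failure is known. The patient also has no surgical specimen from which section 9.1 could read the endpoint, so leaving the patient out of the rate would be easy. If that happened, the feasibility rate would look better than it is.

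**Working it through.** **The plan's own figure.** There is none to reproduce. Section 5.3 says that the 50 was not derived from a hypothesis test, and the protocol gives no expected R0 rate and no drop-out rate. The check is therefore mainly one of text.

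**Step 1: apply the rule to one patient.** Take a patient who is enrolled, starts chemoimmunotherapy, progresses, and is withdrawn before surgery.

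| Reading of section 8.2 | Category of this patient | Result |
|---|---|---|
| Literal, with the randomization condition | Not randomized | Neither sentence applies |
| Intervention is surgery (7.1.2, 8.1, 9.3.1) | Did not receive it | Replaced |
| Intervention includes chemoimmunotherapy (7.1.1) | Received it, then withdrawn | Undecided |

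Three readings give three results. Deleting the randomization condition removes only the first row.

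**Step 2: which failures are affected.** A patient taken to surgery for lobectomy who ends with pneumonectomy has received the intervention on either reading, because section 7.1.1 lists pneumonectomy within it. Only failures before surgery are at issue.

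**Step 3: does enrolment come before therapy?** Sections 5.1 and 7.1.1 say so. Section 1.1 (study interventions) and the third inclusion criterion in 6.1 are less clear. The visit schedule in 7.5 goes from screening to the perioperative period with no column for chemoimmunotherapy. If patients enter only after therapy, failures during therapy never join the sample and replacement is not what hides them.

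**Step 4: size, for illustration only.** Let x be the number of R0 lobectomies among the 50 who remain, and k the number of replaced non-successes. Both are assumed.

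- Rate with replaced patients left out: x/50
- Rate with them counted: x/(50 + k)
- Shift: x/50 − x/(50 + k)

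| x | k = 0 | k = 5 | Shift at k = 5 | k = 10 | Shift at k = 10 |
|---|---|---|---|---|---|
| 30 | 30/50 = 60.0% | 30/55 = 54.5% | 5.5 points | 30/60 = 50.0% | 10.0 points |
| 40 | 40/50 = 80.0% | 40/55 = 72.7% | 7.3 points | 40/60 = 66.7% | 13.3 points |

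The exact (Clopper-Pearson) 95% confidence interval for 40/50 is 66.3% to 90.0%, and for 40/55 it is 59.0% to 83.9%. If replaced patients stay in the denominator, the reported rate is already x/(50 + k) and there is no bias. If the endpoint is R0 among lobectomies, unoperated patients never enter it and replacement does not change it.

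**The case against.** The strongest reply is that the intervention is described, in section 7.1.1, and that the contrary evidence is mixed. Section 7.1.2 only fills in a dosage heading. The list in 8.1 includes radiotherapy and targeted therapy, which section 6.2 excludes before surgery, so it may mean later treatment. Being unable to receive something for a period fits a course of drugs better than one operation. On that reading, replacing subjects who never start is ordinary practice, and only the second sentence is unfinished. This stands in part. It would be wrong to call the intervention undefined; it is described inconsistently. The adverse event definition still points to surgery, and the second sentence still makes no choice.

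A reader might also infer that section 8.2 removes failures from the analysis and so biases the primary result. The text does not say that. Replacement alone removes nobody. Section 8.2 requires the reason for withdrawal on the case report form, and section 11.5.1 expects a list of drop-outs and a step that determines the analysis population. Analysis sets may be in a SAP that is not shown, so their absence is no fault here.

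Nor does the sentence in section 2.4.2 about selecting patients with good results of therapy settle the matter. It may concern the choice of patients for the smaller resection rather than enrolment.

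Finally, the counts in the illustration are assumed and do not measure this trial. That is correct.

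**Conclusion.** The point holds as a defect in a stated rule. Section 8.2 is tied to randomization that does not occur, leaves one category undecided, and turns on a term that the protocol uses in two ways. For a patient withdrawn before surgery, it does not say whether a replacement is enrolled.

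The risk to the primary result is conditional. An upward bias needs all of the following: enrolment before therapy, replacement of patients withdrawn before surgery, their omission from the rate, and a rate not defined as R0 among lobectomies. The documents do not establish that all of these will happen, so a present bias cannot be claimed. Its size is unknown; five omitted non-successes would be worth 5.5 to 7.3 points at the assumed 30 or 40 successes.

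The randomization wording alone is editorial. The open choice matters more, because it can be settled after the failure is known. Section 10.2 lists overall survival as primary instead of the R0 rate; that is a separate conflict to reconcile.

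**What to change.** In section 8.2:
- Delete the randomization condition from both sentences.
- Reconcile sections 7.1.1, 8.1, 8.2 and 9.3.1 on what the study intervention means. Which treatment step counts is for the sponsor to state.
- Replace the open choice with one rule: enrolled subjects who have started neoadjuvant or induction therapy are not replaced, and those withdrawn before surgery count as non-successes in the primary R0-by-lobectomy rate.
- State that only consenting subjects who never start therapy may be replaced, and that they are reported with reasons.

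In section 9.1, make the denominator agree with this rule and report R0 among operated patients as a secondary figure.

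The cost is wording; no new data are needed, since withdrawal reasons are already recorded. The reported rate may be less favourable, and fewer than 50 patients may be operated on. For example, if 5 of 50 do not reach surgery and 36 of the other 45 succeed, the primary rate is 36/50 = 72.0% and the rate among operated patients is 36/45 = 80.0%. Reporting both keeps the surgical result visible.

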### **8.3 Loss of Follow-Up**

Subjects will be followed up for a period of 3 years. Lost visits will be considered to occur when the subject stops scheduled follow-up visits, fails to complete the procedures specified in the study, or cannot be contacted by the investigator.

The investigator will follow the established follow-up plan, complete telephone and outpatient follow-up regularly, and communicate with the subject on a regular basis to minimize lost visits.

## **9. Evaluation of study outcomes**

### **9.1 Evaluation of primary and secondary outcomes**

#### Primary Study Endpoints

R0 Resection rate (lobectomy): the proportion of patients with complete tumor removal by lobectomy, as evaluated by the pathologic findings of postoperative lung cancer specimens;

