**Study Objective :**

Primary objective: to investigate the feasibility of switching to lobectomy after neoadjuvant/induced chemoimmunotherapy in patients with operable non-small cell lung cancer requiring pneumonectomy at first diagnosis (R0 resection rate of lobectomy).

Secondary objective: to investigate the perioperative and long-term outcomes of patients with operable non-small cell lung cancer who were evaluated to undergo pneumonectomy at first diagnosis and switched to neoadjuvant or induction chemoimmunotherapy and subsequent lobectomy.

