### **2.4.2 Assessment of potential risks/benefits**

It has been shown in retrospective studies that total pneumonectomy is only performed when lobectomy is difficult to achieve R0 resection and is associated with higher perioperative complications and mortality than lobectomy, with a significant impact on the patient's general state of health and strength scores, which may contribute to impaired long-term survival. In patients who do well on neoadjuvant or induction therapy, conversion to lobectomy can potentially reduce the incidence of perioperative adverse events, reduce the risk of immediate and long-term non-tumor death, protect the patient's general health and strength scores, and increase the patient's chances of receiving postoperative adjuvant therapy, thereby reducing the risk of tumor-related death.

Risk-minimizing measures: Select patients with good results of neoadjuvant or induction therapy according to strict admission criteria, review the tracheoscopic biopsy before surgery to clarify the status of the bronchus to be preserved, take frozen pathology to clarify the status of the nearest incision margins during the surgery to decide the actual surgical method, and maintain adjuvant therapy after the surgery to minimize the possibility of increasing the risk of local recurrence. Postoperatively, the patient's vital signs, drainage, and air leakage were closely observed to ensure perioperative safety.

Preoperative and intraoperative reassessment

1 Bronchoscopic biopsy of bronchial mucosa to be preserved/EBUS to assess the condition of the outer wall of the preserved bronchus.

2 In cases of main pulmonary artery invasion prior to neoadjuvant therapy, intraoperative

freezing is performed to assess the status of the arterial wall at the site of original invasion.

3 For cases with transverse fissure invasion, pulmonary fissure margins were frozen for pathologic evaluation.

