## 5. Research design

### 5.1 Overall design

In this single-arm, open-label, multicenter, prospective clinical trial, 50 cases of operable non-small-cell lung cancer requiring pneumonectomy were proposed to be enrolled. Patients will be treated with neoadjuvant or inductive combination therapy of immuno- and chemo- by evaluation from multidisciplinary discussion (Department of Thoracic Surgery, department of Respiratory Medicine, department of Radiology), than undergo open or minimally invasive radical surgery for lung cancer and systematic lymph node dissection. Peri-operative complications, lymph node dissection, R0 resection rate, and postoperative short-term and long-term efficacy outcomes will be recorded and evaluated.

Participating centers:

- 1 Ruijin Hospital, Shanghai Jiao Tong University School of Medicine, Shanghai, China
- 2 Shanghai General Hospital of Shanghai Jiao Tong University School of Medicine
- 3 The Ninth People's Hospital of Shanghai Jiao Tong University School of Medicine
- 4 Huadong Hospital, Fudan University Medical College, Shanghai, China

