## **7. Research interventions**

### **7.1 Giving the research intervention**

#### **7.1.1 Description of the research intervention**

After the patients were enrolled in the group, further relevant examinations (bronchoscopy, chest enhanced CT, PET-CT (optional), cranial MR, cardiac ultrasound, pulmonary function, electrocardiogram, and blood test) were completed, contraindications to surgery were ruled out, and they were evaluated to receive neoadjuvant/induced chemo-immunotherapy after multidisciplinary discussion (thoracic surgery, respiratory medicine, pathology). After completion of treatment, the patient is reassessed and discussed multidisciplinary for surgical feasibility. Open or minimally invasive (thoracoscopic-assisted, robotic-assisted) radical lung cancer surgery with systemic lymph node dissection is performed, including

pneumonectomy, lobectomy, combined lobectomy, and sleeve lobectomy (with or without pulmonary angioplasty/sleeve). Based on the surgical pathology and guidelines, the postoperative adjuvant treatment and follow-up plan was individualized after multidisciplinary discussion.

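### The primary endpoint is worded inconsistently and its denominator is not fixed; read as R0 among lobectomies only, it would say little about feasibility of conversion

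*Protocol*

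**What the plan says.** The primary objective in section 1.1 of the protocol is "to investigate the feasibility of switching to lobectomy after neoadjuvant/induced chemoimmunotherapy in patients with operable non-small cell lung cancer requiring pneumonectomy at first diagnosis". The measure attached to it is worded in four places:

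- Section 1.1, Study Objective: "R0 resection rate of lobectomy".
- Section 4: an R0 resection rate, with no mention of lobectomy in the measure.
- Section 5.2: a tumour R0 resection rate with lobectomy in brackets.
- Section 9.1: "the proportion of patients with complete tumor removal by lobectomy, as evaluated by the pathologic findings of postoperative lung cancer specimens".

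On the patient pathway, section 5.1 says that "50 cases of operable non-small-cell lung cancer requiring pneumonectomy were proposed to be enrolled". Sections 5.1 and 7.1.1 place chemoimmunotherapy after enrolment. Section 7.1.1 continues: "After completion of treatment, the patient is reassessed and discussed multidisciplinary for surgical feasibility". It lists pneumonectomy, lobectomy, combined lobectomy and sleeve lobectomy as possible operations.

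The risk-minimising measures in section 2.4.2 (Assessment of potential risks/benefits) are to "Select patients with good results of neoadjuvant or induction therapy according to strict admission criteria", to "review the tracheoscopic biopsy before surgery to clarify the status of the bronchus to be preserved", and to "take frozen pathology to clarify the status of the nearest incision margins during the surgery to decide the actual surgical method".

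Section 8.2 replaces subjects who consented but did not receive the study intervention. It leaves open whether those withdrawn after receiving it are replaced.

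**The concern.** Feasibility of conversion is a question about everyone who starts the pathway needing a pneumonectomy. A patient who progresses, is never operated on, or still has a pneumonectomy is a case in which conversion failed. The protocol does not say that such patients count as non-successes, nor that they are left out.

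The choice matters because of the selection steps. If a positive frozen margin leads the surgeon to a pneumonectomy, that patient leaves the lobectomy group. R0 among completed lobectomies is then conditioned on much of what it is meant to measure. Section 4 errs in the opposite direction: taken literally, an R0 pneumonectomy could count as a success in a study of avoiding pneumonectomy. The replacement rule adds a third route, because a patient who never reaches the intervention may be substituted and drop out of the 50.

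Section 5.3 sets no target rate or hypothesis, so the reader has only the reported rate and its interval to interpret. The meaning of both depends on the denominator.

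**Working it through.** **The plan's own figure.** Section 5.3 gives 50 patients and states that this was not derived from hypothesis testing. There is no calculation to reproduce. The documents give no conversion rate, resection rate or R0 rate among lobectomies, so every count below except 50 is an assumption.

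**Decomposition.** Let N be enrolled, S operated, L lobectomies completed, and x lobectomies with R0. Then

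x/N = (S/N) × (L/S) × (x/L).

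The first two factors describe how often conversion was achieved. The lobectomy-only rate is the last factor alone.

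**Illustration.** Assume N = 50, S = 42, L = 32, x = 31. Intervals are exact (Clopper-Pearson) 95%: lower limit = the 2.5% quantile of Beta(x, n−x+1), upper limit = the 97.5% quantile of Beta(x+1, n−x).

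| Denominator | Rate | 95% CI |
|---|---|---|
| Lobectomies | 31/32 = 96.9% | 83.8 to 99.9 |
| Operated | 31/42 = 73.8% | 58.0 to 86.1 |
| Enrolled | 31/50 = 62.0% | 47.2 to 75.3 |

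Check: (42/50) × (32/42) × (31/32) = 31/50. From first row to last the difference is 96.9 − 62.0 = 34.9 percentage points, with no change in any patient's outcome.

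**Replacement.** If the 50 − 42 = 8 unoperated patients were replaced and dropped, and the replacements fared like the 42, the rate over 50 would be about 73.8% instead of 62.0%, or 11.8 points higher.

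**Section 4 wording.** If the 42 − 32 = 10 pneumonectomies were all R0 (assumed) and counted, the enrolled rate would become 41/50 = 82.0%.

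**Range.** Assume 40 to 50 operated, lobectomy in 40% to 80% of these, and R0 in 95% to 100% of lobectomies, rounded to whole patients. Three of the scenarios:

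| Operated | Lobectomies | R0 | Of lobectomies | Of operated | Of enrolled |
|---|---|---|---|---|---|
| 40 | 16 | 15 | 93.8% (69.8 to 99.8) | 37.5% (22.7 to 54.2) | 30.0% (17.9 to 44.6) |
| 45 | 27 | 26 | 96.3% (81.0 to 99.9) | 57.8% (42.2 to 72.3) | 52.0% (37.4 to 66.3) |
| 50 | 40 | 40 | 100% (91.2 to 100) | 80.0% (66.3 to 90.0) | 80.0% (66.3 to 90.0) |

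Over the whole grid the lobectomy-only rate runs from 93.3% (28/30) to 100%, and the enrolled rate from 30% to 80%. The first range simply returns the R0 assumption put in. What the grid shows is that the lobectomy-only rate does not respond to conversion, while the enrolled rate does.

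**The case against.** A reader might infer that the plan has fixed a lobectomy-only denominator, that conversion failures never enter the rate, and that a result near 100% is close to guaranteed. The documents do not support this.

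- Section 9.1 is the definition, and it can be read as R0 by lobectomy among all patients. On that reading a pneumonectomy or no operation is already a non-success, and frozen section does not inflate the rate. The abstract's wording leans towards the narrow rate but is only a parenthesis.
- Judging R0 on the specimen is not a fault. R0 is a pathological finding, and the clause says how it is assessed, not who is counted.
- The documents give no frozen-section accuracy and no R0 rate among lobectomies. The frozen sections listed cover the nearest margins, the arterial wall at a previously invaded site and the fissure margins, and are not shown to settle final R0.
- Enrolment timing is mixed. Sections 5.1 and 7.1.1 put enrolment before therapy, but section 6.1 describes patients as receiving it and section 2.4.2 speaks of selecting good responders under the admission criteria. If enrolment can follow therapy, an all-enrolled denominator would still miss patients who progressed during it.
- The counts are illustrative, and the three rates share one numerator. That one interval lies above another shows only that the denominator matters.

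All of this stands and limits the claim. It does not remove the inconsistency between sections 1.1, 4, 5.2 and 9.1, or the undefined effect of the replacement rule. A statistical analysis plan may detail analysis sets, but the endpoint definition and the replacement rule are set in the protocol, and its wordings conflict. Section 10.2 does not settle the matter: it lists R0 among secondary endpoints, as a comparison of two groups, with no denominator.

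**Conclusion.** The concern holds as one of definition. The primary endpoint is worded in ways that lead to different quantities, no denominator is named, and the replacement rule could remove conversion failures from the 50. Under the lobectomy-only reading suggested by the abstract, the rate would say little about the stated objective. Under an all-enrolled reading of section 9.1, the endpoint would answer it. The protocol does not choose between them.

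The possible size is large: about 35 percentage points in the illustration, and an enrolled rate anywhere from 30% to 80% beside a lobectomy-only rate of 93% to 100% over the assumed range. These figures rest on assumed counts and are not predictions for this trial. The replacement effect further depends on what the study intervention in section 8.2 means.

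**What to change.** 1. In sections 1.1, 4, 5.2 and 9.1, use one identical definition: patients with pathologically confirmed R0 resection by lobectomy, divided by all enrolled patients. State whether sleeve and combined lobectomy count as lobectomy.
2. Count as non-successes no resection for any reason, pneumonectomy (including intraoperative conversion), and R1 or R2 resection.
3. In section 8.2, state that enrolled patients who do not reach surgery or lobectomy stay in the denominator even if replaced.
4. Reconcile sections 2.4.2, 5.1, 6.1 and 7.1.1 on whether enrolment precedes chemoimmunotherapy, since this decides what all enrolled patients means.
5. Report beside the primary rate the conversion rate (lobectomy completed over enrolled) and the R0 rate among lobectomies, labelling the latter as conditional on intraoperative selection.

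The cost is protocol wording. The counts needed are operation performed, pathological margin status and enrolment status, which the study records anyway. The downside is a less favourable headline rate.
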